### 3.4.4 Handling Missing Data in Descriptive Analyses

When summarizing categorical variables, subjects with missing data are generally not included unless otherwise specified. When needed, the category of "Missing" is created and the number of subjects with missing data is presented.

[figure not shown]
When summarizing continuous variables, subjects with missing data are not included in calculations. No imputations are made.

[figure not shown]
### 3.4.5 Handling Missing or Partially Missing Dates

[figure not shown]
Missing or partially missing dates will not be imputed at data level. However, assumptions for missing or partially missing dates for important variables will be made to allow inclusion of appropriate data records in the analyses. In general, the assumptions about the missing or partially missing dates, when needed, are made conservative to avoid overestimation of treatment effect and underestimation of adverse effects.

If a medication date or time is missing or partially missing, so it cannot be determined whether it was taken prior or concomitantly, it will be considered both as a prior and a concomitant medication.

If the partial AE onset date information does not indicate whether the AE started prior to treatment or after treatment, the AE will be classified as after the start of treatment.

### 4 STUDY SUBJECTS

### 4.1 **DISPOSITION OF SUBJECTS**

The number of subjects randomized and treated, by treatment arm will be presented. The reason for exclusion from one or more analysis sets will be summarized.

The frequency of premature discontinuations from the study treatment prior to Month 12 will be given by treatment arm and overall. The details of the 'Non-fatal Adverse Event', 'Protocol violation', 'Investigator decision', 'Sponsor Decision', 'Subject request', 'Lost to Follow-Up', 'Subject Non-Compliance', 'Death', or 'Other' will be included in a listing.

The frequency of premature discontinuations from the study prior to Month 12 will be given for the ITT and PP populations by treatment arm and overall. The primary reason for non-completion of the study will be summarized.

### 4.2 TREATMENT MISALLOCATIONS

For subjects with errors in treatment allocation, the following is described under which treatment groups they will be reported for efficacy and safety analyses:

For example, if subjects were:

- Randomized (regardless of error) but not treated, then they will be excluded for all efficacy and safety analyses. These subjects will be included in the summary of subject dispositions.
- Treated but not randomized, then by definition they will be excluded from the efficacy analyses since randomization is missing, but will be reported under the treatment they actually received for all safety analyses.
- Randomized but were administered the incorrect treatment at any time during the study, then they will be reported under their randomized treatment group for efficacy analyses on ITT population, but will be reported under the treatment they actually received for all safety analyses on SAFETY population (see Section 3.2.3); specifically, this implies that for safety analyses, a patient who ever received Zimura will be included in the applicable Zimura group based on actual injections received.

### 4.3 PROTOCOL VIOLATIONS

All protocol violations will be assessed and identified prior to database lock in a masked fashion to determine whether they are significant, major, or neither by the sponsor. The final list of major protocol violations will be provided prior to the database lock.

Subjects with significant protocol violations will be excluded from the Per-Protocol Population.

The major protocol violations and significant protocol violations will be summarized for the ITT population. The details will be listed by subject and by treatment arm.

### 4.4 INCLUSION AND EXCLUSION CRITERIA

A frequency table of all inclusion and exclusion criteria not met will be provided for the ITT population by treatment arm and overall. A detailed listing will be provided by subject.

### **5 DEMOGRAPHIC AND OTHER BASELINE CHARACTERISTICS**

Descriptive statistics will be provided to document Baseline and on-trial comparability, including demographic information and treatment administration. No tests of significance will be carried out to compare treatment groups on Baseline data because any observed differences between them must be attributed to chance.

Descriptive statistics with respect to subject characteristics at Baseline will be displayed for the ITT population; if the PP and safety populations are different than the ITT population, demographic data will also be provided for these populations. When several measurements are available before the first administration of study drug, the Baseline value is the last available value prior to first dose, except for the Baseline visual acuity score which is the mean of the screening and Day 1 values, if both are available.

- The variables to be summarized are:
- Gender, ethnicity, race, iris color, age, current smoking status.
- Prior ocular history, both eyes (by MedDRA preferred term, including number and percentage of all subjects with at least one prior ocular history)
- Medical history (excluding ocular history) (by body system and preferred term, with number and percentage for both; including number and percentage of all subjects with at least one prior medical history)
- Prior surgeries/procedures (by body system and preferred term, with number and percentage for both; including number and percentage of all subjects with at least one prior surgery/procedure)
- Vital signs (height, weight, pulse, blood pressure)
- ECOG performance status
- Pregnancy test
- Visual acuity (ETDRS and Snellen equivalent), both eyes
- Low luminance ETDRS, both eyes
- Tonometry, both eyes
- ECG
- Ophthalmic exam, both eyes (motility, lids/lacrimal/lashes, conjunctiva/sclera, cornea, anterior chamber activity: cells, iris, pupils, lens status, vitreous haze, vitreous hemorrhage, posterior vitreous detachment, optic nerve, macula, retinal vessels, peripheral retina)

- Fundus autofluorescence (FAF) imaging assessments, both eyes
  - Localization of hypo FAF (Foveal, Extrafoveal, Ungradeable or no hypo FAF present)
  - Localization of peripapillary atrophy (Temporal only, Nasal and temporal, ungradeable or not applicable)
  - Hyper FAF pattern (Fine granular-punctate spots, Branching, Fine granular-dusty, Trickling, Reticular, Patchy, Banded, Focal, Not determinable/NA)
  - Temporal peripapillary atrophy (N/Y/ungradable or NA)
  - Is peripapillary atrophy confluent with macular GA (N/Y/ungradable or NA)
  - Macular atrophy gradable (N/Y) and reason if not gradable
  - Area of macular atrophy (mm2)
- Fluorescein angiogram (FA) imaging assessment, both eyes
  - Evidence of CNV

### 6 PRIOR AND CONCOMITANT MEDICATION

• All prior and concomitant medications will be summarized separately by WHO Drug code (WHO Drug Dictionary version B2 enhanced March, 2016) on the ITT population. Medication usage will be summarized according to the 2nd level (main therapeutic level) and the 4th level (preferred term level) Anatomic Therapeutic Chemical (ATC) classification. Subjects will only be included once in the summaries within each ATC 2nd level or ATC 4th level category. The summaries will include the number and percentage of all Subjects with at least one prior or concomitant medication, respectively.

### 7 EFFICACY EVALUATION

All efficacy analyses will be conducted for the ITT population. The primary and secondary endpoints will also be conducted for the PP population in a supportive manner.

The analyses will be based on comparisons of Zimura 2 mg vs. the Sham control, and Zimura 4 mg vs. Sham control. For the comparison of Zimura 2 mg vs. Sham control, the subjects randomized from Part 1 will be combined with the subjects randomized to from Part 2, where the analysis will be stratified by Part 1 vs. Part 2. The comparison of Zimura 4 mg vs. Sham control will only based on subjects randomized in Part 2.

The primary analysis will use the ITT population and will be based on a Model for Repeated Measures (MRM) to compare the treatment groups. This analysis provides valid estimates as long as the missing data mechanism fulfills the Missing at Random (MAR) assumption. However, sensitivity analyses (see Section 7.6) will be performed to assess the potential magnitude and direction of the impact of missing data. Although Zimura 1 mg dose is not of an interest, a

descriptive analysis for a treatment effect of Zimura 1 mg dose vs. Sham control will be conducted in a supportive manner.

The primary analysis **and the set of** for each of the two pairwise comparisons of an active dose of Zimura vs the Sham control is formally based on a three-category decision guideline. The decision guideline for this trial is based on whether the estimated mean reduction in rate of square root of GA area growth over 12 months for a dose of Zimura versus Sham control is less than 14%, is from 14% up to 24.5%, or is at least 24.5%. These numbers may be adjusted based on the final sample size and standard deviation.

- 1. If the estimated reduction in the rate of GA growth over 12 months for a dose of Zimura vs. Sham control is less than 14%, then this dose of Zimura is not plausibly more efficacious than the Sham control; its utility in this indication should be reconsidered.
- 2. If the estimated reduction in the rate of GA growth over 12 months for a dose of Zimura vs. Sham control is from 14% to up to 24.5%, then this dose of Zimura is plausibly more efficacious than the Sham control and should be evaluated in a subsequent Phase 3 clinical trial.
- 3. If the estimated reduction in the rate of GA growth over 12 months for a dose of Zimura vs. Sham control is at least 24.5%, then this dose of Zimura would be statistically significantly more effective than the Sham control, with strength of evidence meeting the standard requirement of a 0.0125 one-sided false positive error rate (incorporating an adjustment for multiplicity arising from comparing each dose with the Sham control).

Note that these categories should not be interpreted as providing strict decision rules but rather as guidelines that will be factored into a broader scientific assessment of the benefit to risk profile of the Zimura dose regimen.

### 7.1 CONTROL OF ALPHA

The overall (one-sided) false positive error rate in this trial, accounting for the conduct of two pairwise comparisons (2 mg and 4 mg) with Sham control, is 0.025 for the analysis of the primary endpoint. The actual test of each dose *vs*. sham will use a Hochberg procedure for significance testing.

[figure not shown]
An analysis of secondary endpoints will be carried with a descriptive intent only, without alphaadjustment.

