1. If the estimated reduction in the rate of GA growth over 12 months is less than 14%, then this dose of Zimura™ is not plausibly more efficacious than the Sham control; its utility in this indication should be reconsidered.
2. If the estimated reduction in the rate of GA growth over 12 months is from 14% to up to 24.5%, then this dose of Zimura™ is plausibly more efficacious than the Sham control and should be evaluated in a subsequent Phase 3 clinical trial.

In planning the design of the confirmatory Phase 3 trials, this trial (and other information that emerges during the conduct of this trial) will provide important insights through consideration of:

- a. The estimated benefit-to-risk profile of this dose of Zimura™;
  - b. Possible refinements in the dose/schedule of Zimura™
  - c. Approaches to improve adherence to the Zimura™ regimen;
  - d. Modifications to defining eligibility criteria to enhance enrichment;
  - e. Approaches to achieving timely accrual of study participants at centers with established ability to provide high quality implementation of the trial and high quality data.
3. If the estimated reduction in the rate of GA growth over 12 months is at least 24.5%, then this dose of Zimura™ would be statistically significantly more effective than the Sham control, with strength of evidence meeting the standard requirement of a 0.0125 one-sided false positive error rate (incorporating an adjustment for multiplicity arising from comparing each dose with the Sham control).

The operating characteristics for this three-category decision guideline are:

1. The false-positive error rate of the screening procedure is low. In particular, if a given dose of Zimura™ truly provides no improvement in the rate of GA growth over 12 months, then there is only a 10% chance of bringing that dose forward to a Phase 3 trial and only a 1.25% chance of reaching the false positive conclusion that that dose regimen provides a statistically significant improvement in efficacy relative to a Sham control. Given that there will be two pairwise comparisons, if both doses of Zimura™ truly provide no improvement in the rate of GA growth over 12 months, then the probability of achieving a false positive conclusion for further study for at least one dose regimen likely would be in the range of 15% to 17% (when one takes into account the positive correlation between these two

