assessments), and the probability of reaching a conclusion that at least one dose regimen provides a statistically significant improvement in efficacy relative to a Sham control is only 2.5%.

2. The false-negative error rate is low. If a given dose of Zimura™ truly provides a 28% reduction in the rate of GA growth over 12 months, then there is only a 10% chance that that dose of Zimura™ would be discarded, and thus a 90% chance that it would be evaluated in a subsequent confirmatory Phase 3 trial. Given that there will be two pairwise comparisons, if both doses of Zimura™ truly provide a 28% reduction in the rate of GA growth over 12 months, then it is likely (when one takes into account the positive correlation between these two assessments) that there is at least a 95% chance that at least one dose would be evaluated in a subsequent confirmatory Phase 3 trial. If a given dose of Zimura™ truly provides a 28% reduction in the rate of GA growth over 12 months, there is a 63% chance that that regimen will have a statistically significant improvement in efficacy (at one-sided  $p < 0.0125$ ) relative to the Sham control.

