### **11.6.2 Significance Levels**

The overall (one-sided) false positive error rate in this trial, accounting for the conduct of two pairwise comparisons with Sham control, is 0.025 for the analysis of the primary endpoint.

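### SAP 7.1 tests the doses with Hochberg, but category 3 and the protocol's 1.25% and 63% describe a fixed one-sided 0.0125 test per dose, so a significant dose can sit in category 2

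*SAP*

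**What the plan says.** SAP 7.1 sets the overall one-sided false-positive rate over the two comparisons; it "is 0.025 for the analysis of the primary endpoint". The test of each dose against "sham will use a Hochberg procedure for significance testing". Protocol 11.6.2 gives the same overall rate and names no multiplicity procedure.

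SAP 7 then sorts each dose into one of three categories by its estimated reduction in growth rate. In category 3, if the reduction is "at least 24.5%, then this dose of Zimura would be statistically significantly more effective than the Sham control", this is "with strength of evidence meeting the standard requirement of a 0.0125 one-sided false positive error rate". In category 2, the reduction "is from 14% to up to 24.5%, then this dose of Zimura is plausibly more efficacious than the Sham control and should be evaluated" in Phase 3. Protocol 11.3 has the same categories, and the third bullet of Protocol 11.1 uses the same 0.0125 standard. Both documents call the categories guidelines rather than strict rules. The SAP also allows the cut-offs to be adjusted for the final sample size and standard deviation.

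Protocol 11.3 gives these operating characteristics: for a dose with no effect, "only a 1.25% chance of reaching the false positive conclusion that that dose regimen provides a statistically significant improvement"; for a dose with a true 28% reduction, "there is a 63% chance that that regimen will have a statistically significant improvement in efficacy", labelled as one-sided p < 0.0125.

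**The concern.** With two doses, Hochberg at overall one-sided 0.025 rejects both when the larger p-value is at most 0.025. Otherwise it tests only the smaller one, at 0.0125. The bar for one dose therefore depends on the other dose's result, and a single percentage cut-off cannot represent that. The permitted adjustment of the cut-offs does not help, because it covers sample size and standard deviation only.

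Two things are at stake. A dose can be significant under the test in SAP 7.1 while SAP 7 files it under the category below the one described as significant. And the per-dose error rate and power in Protocol 11.3 do not describe the test that will be run. Protocol 11.3 also makes the 18-month assessment conditional on significance at 12 months, so it helps to have one definition of significance throughout.

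**Working it through.** **Inputs.** Cut-offs of 14% and 24.5%, with null probabilities of 10% and 1.25% and a true effect of 28% (Protocol 11.3). Arm sizes (Protocol 11.3): 26 v 26 in Part 1 and 40 v 80 in Part 2 for 2 mg; 80 v 80 for 4 mg. Overall one-sided 0.025 with Hochberg (SAP 7.1). No SD is stated.

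**Step 1: planned standard error (SE), from the cut-offs.**
- 24.5 / z(0.9875) = 24.5 / 2.241 = 10.93 points
- 14 / z(0.90) = 14 / 1.282 = 10.92 points

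The two agree.

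**Step 2: reproduce the plan's figures with a fixed 0.0125 per dose.**
- P(estimate ≥ 24.5% | no effect) = 1.25% (stated 1.25%)
- P(estimate ≥ 24.5% | 28%) = Φ((28 − 24.5)/10.93) = 62.6% (stated 63%)
- P(estimate ≥ 14% | 28%) = Φ((28 − 14)/10.93) = 90.0% (stated 90%)

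So the stated 1.25% and 63% are those of the fixed rule.

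**Step 3: the Hochberg bars.** A dose on its own needs 2.241 × 10.93 = 24.5%. If both doses clear it, the bar is 1.960 × 10.93 = 21.4%. If the SE changes, both bars scale together (ratio 1.960/2.241 = 0.87), so rescaling the cut-offs leaves the gap.

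Example: 4 mg at 26% has z = 26/10.93 = 2.38, p = 0.009. 2 mg at 22% has z = 22/10.93 = 2.01, p = 0.022. Both are Hochberg-significant, and 2 mg is in category 2.

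**Step 4: correlation of the two tests** (equal SD, inverse-variance weighting of the Parts, only the Part 2 Sham arm shared).
- Information, in units of 1/SD²: 2 mg, 13 + 26.67 = 39.67; 4 mg, 40
- Weight of Part 2 in the 2 mg estimate: 26.67/39.67 = 0.672
- Correlation: (0.672/80) × √(39.67 × 40) = 0.335

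**Step 5: Hochberg operating characteristics** (bivariate normal).
- Per-dose rejection = P(Z₁ ≥ 2.241) + P(1.960 ≤ Z₁ < 2.241 and Z₂ ≥ 1.960)
- Overlap (at least one significant dose in category 2) = P(both ≥ 1.960) − P(both ≥ 2.241)

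| True effects | Per dose, fixed 0.0125 | Per dose, Hochberg | Overlap |
|---|---|---|---|
| Both 28% | 62.6% | 62.6 + 6.9 = 69.4% (unrounded sum) | 12.6% |
| One 28%, one null: null dose | 1.25% | 1.25 + 1.15 = 2.4% | 1.2% (per trial) |
| One 28%, one null: working dose | 62.6% | 62.7% | as above |
| Both null | 1.25% | 1.25 + 0.11 = 1.36% | 0.2% |

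For correlations from 0 to 0.5, the ranges are: both at 28%, power 69.3% to 69.9% and overlap 12.2% to 13.6%; null dose beside a working one, 2.2% to 2.5%; both null, 1.28% to 1.43% per dose. As the other dose's effect grows, the null dose's rate approaches its ceiling of 2.5%.

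**Step 6: overall error, both doses null.** P(at least one rejection) is 2.46% under Hochberg (2.40% to 2.50% over the same correlations), within 2.5%.

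**Step 7: how far the trial-level result moves, both at 28%.** P(at least one significant dose) is 81.0% under the fixed rule and 82.1% under Hochberg. Both doses lie in the 21.4% to 24.5% band in 1.1% of trials. Only then is there a significant dose with none in category 3.

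**The case against.** The strongest defence is that the documents do not contradict each other outright. SAP 7.1 identifies Hochberg as the actual test, and the categories are guidelines. Category 3 reads as a sufficient condition, which at the planned SE is always true under Hochberg, since any p-value at or below 0.0125 is rejected. Category 2 never says the dose is not significant. The practical difference is also small: Protocol 11.1 expects a confirmatory trial even after a significant result. All of this stands.

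A reader might infer more than the documents support:
- *That the headline conclusion depends on which section is read.* SAP 7.1 indicates which rule governs significance. What is missing is category wording that agrees with it.
- *That the overall error rate is inflated.* It is not (step 6).
- *That 63% is wrong.* It is correct for the p < 0.0125 test it names; it understates Hochberg power only when both doses work.
- *That 12.6% is the general chance of overlap.* It is the case where both doses work. In most of those trials the other dose is already in category 3, so only the second dose's label is affected.

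The 1.25% figure is not rescued by these points. It is presented as the chance of a false claim of significance for a dose, and under SAP 7.1 that chance is higher. Nor does guideline status cover the error rate stated inside category 3, or Protocol 11.1's presentation of the three outcomes as alternatives.

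**Conclusion.** The mismatch is real and modest. Category 3, Protocol 11.1 and the per-dose figures in Protocol 11.3 describe a fixed 0.0125 test, while SAP 7.1 specifies Hochberg. The practical result is a band from 21.4% to 24.5% in which a dose is significant but in category 2 if the other dose also reaches 21.4%, and a stated per-dose false-positive rate of 1.25% that should read about 1.4% to at most 2.5%. It should be fixed, but it does not threaten the validity of the primary test.

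The figures assume normal estimates, an SE of the percentage reduction that is equal for both doses and the same under null and alternative, full planned arm sizes without dropout, and the back-solved SE. The planned arms support near-equal precision (39.67 v 40). The mismatch itself does not depend on the SE; the percentages do.

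**What to change.** Keep Hochberg and align the rest with it before unmasking:

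1. State in SAP 7 and Protocol 11.3 that the Hochberg procedure of SAP 7.1 alone determines statistical significance.
2. Define category 3 as rejected by that procedure, and category 2 as an estimated reduction of at least 14% but not rejected.
3. In SAP 7, Protocol 11.3 and the third bullet of Protocol 11.1, replace the phrase "with strength of evidence meeting the standard requirement of a 0.0125 one-sided false positive error rate" (or its equivalent there) with: significant under Hochberg at overall one-sided 0.025. If the phrase stays, a dose with p = 0.022 would be in category 3 and described as meeting 0.0125.
4. Give 24.5% (dose on its own) and 21.4% (both doses clear it) as planning values only.
5. Restate the per-dose false-positive rate as about 1.4% with both doses null and at most 2.5%, and power as 63% if one dose works and about 69% if both do. Leave the overall 2.5% as it is.

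Testing each dose at a fixed 0.0125 would also make the documents agree and would keep 1.25% and 63%, but it would give up the extra power when both doses work.

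The cost is wording in two documents, with no added patients or data. The stated per-dose false-positive rate becomes slightly less favourable.

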### 7.2 ANALYSIS OF PRIMARY EFFICACY ENDPOINT

The primary efficacy endpoint is mean rate of change in GA over 12 months measured by fundus autofluorescence (FAF) at three time points: Baseline, Month 6, and Month 12. To eliminate the dependency of GA growth rates on the Baseline lesion size (Feuer et al., 2013), instead of using the observed GA area measurement, the square root of the GA area will be used in the analysis.

For analyses of the primary endpoint, a Mixed-Effects Repeated Measures (MMRM) model will be used to assess the differences between the treatment groups in rate of change of GA area over 12 months. Two separate models will be fitted for comparing Zimura 4 mg vs. Sham control, and Zimura 2 mg vs. Sham control. Both models will be fitted by using restricted maximum likelihood (REML) and include Baseline VA (< 50 letters vs.  $\geq 50$  letters), size of the Baseline GA (< 4 disc area vs.  $\geq$  4 disc area), and pattern of FAF at the junctional zone of GA (none/focal vs. banded/diffuse) as used in the randomization as covariates. For Zimura 2 mg vs. Sham control model, fixed effects will include treatment, visit, part (Part 1 vs. Part 2), the Baseline VA (< 50 letters vs.  $\geq$  50 letters), size of the Baseline GA (< 4 disc area vs.  $\geq$  4 disc area), pattern of FAF at the junction zone of GA (none/focal vs. banded/diffuse), treatment by visit interaction, and the stratification factors by visit interactions. For Zimura 4 mg vs. Sham control model, the same fixed effects will be used excluding part (Part 1 vs. Part 2). An unstructured (co)variance structure will be used to model the within-subject errors. If this analysis fails to converge, alternative structures (e.g., heterogeneous autoregressive or heterogeneous compound symmetry, in this order) will be considered. The Kenward-Roger approximation will be used to estimate denominator degrees of freedom. The test of the mean rate of change over 12 months will be assessed by testing the appropriate contrast of the model parameter estimates.

In addition to the analyses described above, a similar analysis will be conducted using the observed GA area measurement.

The analyses described above will also be repeated in a supportive manner for the PP population.

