### 11.3 Determination of Sample Size and Statistical Rationale

The sample size determination for this study is based on [REDACTED] screening methodology presented in Fleming and Richardson (2004). The power calculations are based on the recently released results from a clinical trial of a complement inhibitor, including the estimated precision of the estimated effects on rate of GA growth over 12 months, and including the plausible effect size for Zimura™.

A total of approximately 277 subjects will be enrolled. When follow-up is complete for the primary analysis based on 12-month follow-up, the data base will be locked. Information post-12 months will remain fully confidential until completion of 18-month follow-up. By pre-specification, a hierarchical analysis will be performed where the treatment effect on the rate of GA growth over 18 months will be statistically assessed if statistical significance is achieved on the rate of GA growth over 12 months.

[REDACTED] the primary analyses will be based on comparisons of Zimura™ 2 mg vs the Sham control, and Zimura™ 4 mg vs Sham control. For the comparison of Zimura™ 2 mg vs Sham control, the 26 subjects randomized to Zimura™ 2 mg and 26 subjects randomized to Sham control from Part 1 will be combined with the 40 subjects randomized to Zimura™ 2 mg and 80 subjects randomized to Sham control from Part 2, where the analysis will be stratified by Part 1 vs Part 2. The comparison of Zimura™ 4 mg vs Sham control will be based on the 80 subjects randomized to each of these two arms in Part 2.

The primary analysis [REDACTED] for each of the two pairwise comparisons of an active dose of Zimura™ vs the Sham control is formally based on a three-category decision guideline. To be specific, the decision guideline for this trial is based on whether the estimated reduction in rate of GA growth over 12 months for a dose of Zimura™ versus Sham control is less than 14%, is from 14% up to 24.5%, or is at least 24.5%.

Note that these categories should not be interpreted as providing strict decision rules but rather as guidelines that will be factored into a broader scientific assessment of the benefit to risk profile of the Zimura™ dose regimen. This broader assessment will include consideration of safety, of supportive efficacy endpoints, and of relevant information external to this trial. Specifically, the decision guidelines for this trial are:

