#### **11.4 Randomization Procedure**

Subjects will be centrally allocated to one of the three treatment groups stratified by factors known to be of prognostic importance in dry AMD:

- Baseline visual acuity < 50 ETDRS letters (20/100 Snellen equivalent) vs  $\geq$  50 ETDRS letters
- Size of baseline geographic atrophy (< 4 disc areas vs  $\geq$ 4 disc areas)
- Pattern of Fundus Auto Fluorescence (FAF) at the junctional zone of GA (None/focal vs banded/diffuse)

Randomization will be performed using an IRT system based on the stratification information above to randomize each subject and assign a treatment arm.

The IRT system will be used to assign masked study kits to subjects throughout the duration of the trial. All study medication must be dispensed using the IRT system. At each dispensing visit the IRT system will allocate each study drug kit(s) using the kit number on the label of the study medication kit.

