### 2.3 RANDOMIZATION

[figure not shown]
Subjects will be centrally allocated to one of the three treatment groups stratified by factors known to be of prognostic importance in dry AMD:

- Baseline visual acuity < 50 ETDRS letters (20/100 Snellen equivalent) vs. ≥ 50 ETDRS letters
- Size of Baseline geographic atrophy (< 4 disc areas vs.  $\geq$  4 disc areas)
- Pattern of FAF at the junctional zone of GA (None/focal vs. banded/diffuse)

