### 3.2.1 Intention-To-Treat (ITT) Population

The intention-to-treat population (ITT) will consist of all randomized subjects who received at least one dose of study drug, irrespective of the dose actually received. Subjects will be analyzed in the treatment group assigned at randomization. Subjects will be included in a particular analysis, for a particular population, if relevant data is available for analysis (e.g., the primary analysis will require both Baseline and at least one post-Baseline GA measurement, to calculate a change score).

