### 7.7 SUBSET ANALYSES

The trial is not sized to test for the presence of treatment by subset interactions. Thus, true treatment by subset interactions will likely be missed, unless they are quite substantial. Conversely, should any particular subset of subjects seem to benefit more or less from therapy than the total population, this will not be taken as evidence of a true treatment by subset interaction, given the likelihood that such an observation could be due to chance alone. With these caveats in mind, exploratory subset analyses will be performed to identify any major effect that might be worth testing in future trials. Clinically meaningful subsets will be looked at, including stratification factors: Baseline visual acuity (< 50 vs.  $\geq$  50 ETDRS letters), Baseline geographic atrophy (<4 vs.  $\geq$  4 disc area), Pattern of Fundus Auto Fluorescence at the junctional zone of geographic atrophy (none/focal vs. banded/diffuse).

These analyses will be considered as supportive efficacy analyses and conducted without any alphalevel adjustment.

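### The SAP's primary model for 2 mg vs Sham names no Part-by-visit term, so on one reading the 12-month rate contrast is not fully stratified by Part

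*SAP*

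**What the plan says.** Both documents promise stratification by Part for the 2 mg comparison. Protocol 11.3 pools the two Parts' 2 mg and Sham subjects, ending with the 80 "subjects randomized to Sham control from Part 2, where the analysis will be stratified by Part 1 vs Part 2". SAP 7 repeats it: "where the analysis will be stratified by Part 1 vs. Part 2".

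SAP 7.2 turns this into a model. For 2 mg vs Sham the fixed effects are treatment, visit, Part, baseline VA, baseline GA size, FAF pattern, treatment by visit, and by-visit terms for the stratification factors. The text at that point reads "and the stratification factors by visit interactions. For Zimura 4 mg vs. Sham control model". The 4 mg model is then formed by dropping Part: "the same fixed effects will be used excluding part (Part 1 vs. Part 2". A Part-by-visit term is not named in either sentence.

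The stratification factors are listed in three places. SAP 2.3 ("stratified by factors known to be of prognostic importance in dry AMD") and Protocol 11.4 give VA, GA size and FAF pattern. SAP 7.7 begins the same list with "Clinically meaningful subsets will be looked at, including stratification factors: Baseline visual acuity" and goes on to GA size and FAF pattern. Part is in none of them.

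On the form of the response, SAP 3.2.1 says "the primary analysis will require both Baseline and at least one post-Baseline GA measurement, to calculate a change score".

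**The concern.** The primary quantity is a rate of growth over 12 months. A Part main effect adds the same constant at every visit, so it cannot in general absorb a difference between Parts in how fast lesions grow. A Part-by-visit term can.

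Part is also unbalanced across the arms by design. The 2 mg to Sham allocation is 1:1 in Part 1 and 1:2 in Part 2. Randomization within each Part does not protect the pooled contrast; only adjustment does. Protocol 6 states that Part 1 recruitment was complete as of Amendment C, which suggests that the Parts were recruited in sequence, although no start date is given for Part 2. A difference in growth between them is therefore possible.

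At stake is one of the two primary contrasts. If the statistician programming SAP 7.2 takes the stratification factors to be the three listed elsewhere, any residual Part difference in growth biases the 2 mg estimate in a direction nobody can know in advance. The 4 mg comparison uses Part 2 only and is unaffected.

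**Working it through.** **Inputs.** From Protocol 11.3: cells of 26 (2 mg) and 26 (Sham) in Part 1, 40 and 80 in Part 2; cut-offs of 14% and 24.5%; one-sided error 0.0125; 63% power at a 28% reduction. Assumed, because the documents do not give them: D, the Part difference in 12-month growth left after the root transformation and the other covariates, as a percentage of the Sham rate (5, 10, 20, 30); the ratio of the Month 6 to Month 12 SD (0.5 to 0.8); and the correlation between the two changes (0.5 to 0.9). Data are taken as complete and growth as linear.

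**1. Reproduce the plan's own figures.** The SE implied by the cut-offs is 24.5/2.241 = 10.93 and 14/1.282 = 10.92 percentage points, which agree. Power at 28% is Φ(28/10.93 − 2.241) = 62.6%, against 63% stated.

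**2. Imbalance.** Part 1 share: 26/66 = 39.4% of 2 mg and 26/106 = 24.5% of Sham. The gap is 0.3939 − 0.2453 = 0.1487.

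**3. Bias of the 12-month contrast.** This is the expected generalized least squares estimate in the four cells, with a Part effect of D/2 at Month 6 and D at Month 12.

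| Response | Part main effect only | With Part by visit |
|---|---|---|
| Change from Baseline at Months 6 and 12 | 0.053D to 0.122D | 0 |
| Root-area levels at three visits | 0.149D | 0 |
| Change per unit time | 0 | 0 |

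With levels, the constant Part effect cancels from the Month 12 minus Baseline contrast, so the whole imbalance passes through. With change scores it absorbs part of the difference. With change per unit time under linear growth, the Part effect is itself constant and is removed entirely.

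**4. Consequence for the change-score response.** Error rate at the 24.5% cut-off: 1 − Φ(2.241 − bias/10.93). Chance of passing the 14% cut-off under no effect: 1 − Φ((14 − bias)/10.93). The bias favours 2 mg if Part 1 grows more slowly; if Part 1 grows faster, its sign is reversed.

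| D (%) | Bias (points) | 1.25% becomes, favouring 2 mg | 1.25% becomes, against 2 mg | 10% becomes, favouring 2 mg | 10% becomes, against 2 mg |
|---|---|---|---|---|---|
| 5 | 0.3–0.6 | 1.3–1.4% | 1.1–1.2% | 10.4–11.0% | 9.1–9.6% |
| 10 | 0.5–1.2 | 1.4–1.7% | 0.9–1.1% | 10.9–12.1% | 8.2–9.2% |
| 20 | 1.1–2.4 | 1.6–2.2% | 0.7–1.0% | 11.8–14.5% | 6.6–8.4% |
| 30 | 1.6–3.7 | 1.8–2.8% | 0.5–0.9% | 12.8–17.2% | 5.3–7.7% |

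For the 1.25% rate to reach 2%, D must be (2.241 − 2.054) × 10.93/k, which is 16.8 for k = 0.122 and 38.7 for k = 0.053. With three-visit levels (0.149D), the favourable-direction rates are about 1.5%, 1.8%, 2.4% and 3.3%.

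**5. Cost of the term.** Information for 80:80 is 80 × 80/160 = 40.00; for 66:106 unstratified, 66 × 106/172 = 40.67; stratified by Part, 26 × 26/52 + 40 × 80/120 = 39.67. The SEs are 10.93 × √(40/40.67) = 10.84 and 10.93 × √(40/39.67) = 10.98, a rise of 1.3% (0.4% to 1.1% for a change score). Power Φ(28/SE − 2.241) goes from 63.4% to 62.2%.

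**The case against.** The text allows a reading with no defect. The 2 mg sentence in SAP 7.2 lists Part beside the three prognostic factors and then refers to stratification factors. SAP 7 calls the analysis stratified by Part, which could make Part one of them. When SAP 7.2 means only the randomization factors, the sentence before ties them to the randomization; the 2 mg sentence does not. Dropping Part for the 4 mg model may be shorthand for dropping its interaction too. Neither Protocol 11.3 nor SAP 7 says that stratification requires a by-visit term. This stands as far as it goes: the point is an ambiguity, not a proven error. It does not settle the wording, because everywhere the factors are listed Part is missing.

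The size rests on an unknown D, and nothing in the documents shows that growth differs by Part. For small D the simpler model even has the lower mean squared error: up to roughly 10% to 21% of the Sham rate for a change score, or for levels √(10.98² − 10.84²)/0.149, about 12%. That also stands, but it is an argument for a different model, not for leaving the promised one unclear.

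The consequence is limited in other ways. The cut-offs are guidelines and may be adjusted (SAP 7). Under the Hochberg procedure (SAP 7.1), 0.0125 is the operative level only when the other dose misses 0.025. SAP 3.3 provides a forest plot by Part, which would show the within-Part comparisons but would not correct the pooled primary contrast.

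**Conclusion.** The point holds and is minor. SAP 7.2 names no Part-by-visit term, and on the list of stratification factors given elsewhere in the documents the 2 mg rate contrast is only partly adjusted for Part. If the phrase was meant to include Part, the model already does what SAP 7 promises.

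On the narrower reading, with the change-score response that SAP 3.2.1 points to, the bias is 0.02 to 0.33 standard errors for an assumed D of 5% to 30% of the Sham rate. It is zero if D is zero, and its direction is unknown. These figures assume complete data, linear growth and the covariance ranges above, with the SE taken back from the plan's own cut-offs. The plan's sample size and stated power need no change. Confidence is medium, because both the intended reading and D are unknown.

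**What to change.** In SAP 7.2, name Part by visit among the fixed effects of the 2 mg vs Sham model. Use the same wording for the 2 mg model in SAP 7.3, for consistency only, since those analyses are exploratory. The term removes the bias under each of the three response forms considered, so no separate change to the response definition is needed for this point.

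The change is one named term, to be made before unmasking. If the broader reading was intended, it costs nothing statistically. Otherwise it costs the small loss of precision shown in step 5, about one point of power, and the result still agrees with the stated 63%.
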